10.3 Subgroup Analyses

Exploratory subgroup analyses of the primary, secondary and exploratory analyses may be performed. These may include:

- Subgroup analyses by severity of the patients' SARS-CoV-2 infection using groupings of the WHO ordinal scale of COVID severity as data allow
- Subgroup analyses by COVID vaccine status

11. SAFETY AND TOLERABILITY ANALYSES

The safety analyses will be run on the Safety population. The analysis of safety in this study will include summaries of the following safety and tolerability data collected for each patient:

- Adverse Events
- Clinical Laboratory Investigations
- C-SSRS
- Vital Signs
- Physical Examinations and examinations of the oral cavity

11.1 Adverse Events

All AEs, TEAEs, and SAEs will be coded using a current version of the MedDRA Dictionary.

The collection of adverse events will begin at the time the patient is consented and screened for the study. Treatment-emergent adverse events (TEAEs) are defined as either new onset AEs with an onset at the time of or following the start of treatment, as indicated by a “no” answer to “Did AE start prior to the first dose?”, or a recurrence of an AE (or medical history) present prior to randomization but increasing in severity, frequency or relationship at the time of or following the start of treatment.

An AE summary table will be presented for the following:

- All TEAEs
- TEAEs by severity
- TEAEs leading to study drug discontinuation
- TEAEs by relationship
- SAEs
- Oral cavity TEAEs
- Oral cavity TEAEs by severity

Summaries of incidence rates (frequencies and percentages), of individual AEs by MedDRA SOC and preferred term will be prepared. Such summaries will be displayed for all TEAEs, oral cavity TEAEs, TEAEs by maximum severity, and TEAEs by strongest relationship to study drug.

Each patient will be counted only once within each summation level (SOC; preferred term). If a patient experiences more than one TEAE within each summation level, the TEAE with the strongest relationship or the maximum severity, as appropriate, will be included in the summaries of relationship and severity.

In the AE data listings, all AEs will be displayed. AEs that occur prior to randomization will be considered pre-treatment AEs, and will be determined by a “yes” response to the CRF question, “Did the AE start prior to the first dose?” AEs that start on the date of randomization but have a “yes” response to this question will be categorized as pre-treatment AEs. TEAEs will be defined from the date of randomization and a “no” response to the CRF question, “Did the AE start prior to the first dose?”

11.1.1 Adverse Events Leading to Discontinuation of Study Drug

A data listing of AEs leading to discontinuation of study drug will also be provided, displaying details of the event(s) captured on the CRF.

11.1.2 Serious Adverse Events

A data listing of SAEs will also be provided, displaying details of the event(s) captured on the CRF.

11.1.3 Oral TEAEs

In light of the study drug's sublingual route of delivery, patients will undergo a detailed examination of the oral cavity at screening and brief examinations at all other visits.

AEs involving the oral cavity may be spontaneously reported by the patient, observed during an oral cavity examination, or both. Oral cavity AEs will be identified by a "yes" response to the CRF question, "Is the AE in the oral cavity?" Additional information will be collected on oral cavity AEs (based on a "yes" response to the above question), including whether the AE occurs immediately or very soon after dosing, an approximation of the duration of the AE (less than or greater than 60 minutes), and whether the AE is still present the next morning upon awakening.

A separate by-patient listing of oral cavity AEs (including pre-treatment oral cavity AEs) will be provided.

11.1.4 Deaths

A listing of deaths will also be provided for the Safety Population.

11.2 Clinical Laboratory Evaluations

Laboratory values will be displayed in the data listings with their corresponding normal ranges, and those values that are outside the normal range will be flagged.

A by-patient listing of all clinical laboratory (Chemistry, Hematology and Urinalysis) data will also be provided.

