7.2.4. Safety

- Incidence of AEs
- Changes from Baseline in clinical laboratory tests
- Changes from Baseline in vital signs
- Assessment of physical examination findings, including examinations of the oral cavity
- Monitoring suicidality using Columbia-Suicide Severity Rating Scale (C-SSRS)

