12.2.6. Clinical Laboratory Assessments

The clinical laboratory evaluations to be performed in this trial are listed in [Table 3](#). Those marked as screening tests will be performed at Screening only. All other tests will be performed at the Screening Visit, Visit 4/Week 6, and at Visit 6/ET (Week 14), aside from urine pregnancy tests and ad hoc urine drug screens. Testing for HIV, HCV, and hepatitis B surface antigen (HBsAg) will be performed at Screening and may be performed at other visits at Investigator’s or Sponsor’s discretion.

With the exception of the urine pregnancy test or an ad hoc urine drug screen, all clinical laboratory evaluations will be analyzed via a central clinical laboratory, and information regarding appropriate sample volume, collection tubes, sample labeling and handling, and shipment will be provided in the clinical laboratory manual.

As per Exclusion Criterion #14 any patient with evidence during the preceding year of drug or alcohol use disorder by MINI or history is ineligible.

A centrally analyzed UDS will be performed at Visit 1. If the patient has a positive drug screen at Visit 1 due to a drug of abuse (eg, cocaine, methamphetamine, ecstasy) or due to a non-disclosed opioid, amphetamine, or benzodiazepine, then he/she should be screen-failed. As discussed in [Section 9.2](#), patients utilizing cannabis/THC are to be excluded if MINI criteria are met for greater than MILD Cannabis Use Disorder during the preceding 12 months, OR if the Investigator is concerned that the patient's use of cannabis/THC could interfere with patient's ability to provide reliable data or comply with the protocol. Otherwise, patients utilizing cannabis or THC products are allowed, with caution.

The screening drug screen will test for THC to provide the Investigator with information regarding exposure, and to ensure that all usage is disclosed and taken into consideration when conducting MINI Module J. Repeat testing of THC is not necessary for patients testing positive for cannabis/THC at screening.

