13.7. Safety Analyses

Safety analyses will be performed using the Safety Population. The analysis of safety assessments in this study will include summaries of the following safety and tolerability data collected for each patient:

- Incidence of AEs
- Changes from Baseline in clinical laboratory tests
- Changes from Baseline in vital signs
- Changes from Baseline in physical examination findings including examination of the oral cavity
- Monitoring suicidality using the C-SSRS

All AEs, treatment-emergent adverse events (TEAEs), and SAEs will be coded using the MedDRA.

An AE summary table will be presented for the following:

- All TEAEs
- TEAEs by severity
- TEAEs leading to study drug discontinuation
- TEAEs by relationship
- SAEs
- Oral cavity TEAEs
- Oral cavity TEAEs by severity

Summaries of incidence rates (frequencies and percentages), of individual AEs by MedDRA SOC and preferred term will be prepared. Such summaries will be displayed for all TEAEs, oral cavity TEAEs, TEAEs by maximum severity, and TEAEs by strongest relationship to study drug.

Each patient will be counted only once within each summation level (SOC; preferred term). If a patient experiences more than one TEAE within each summation level, the TEAE with the strongest relationship or the maximum severity, as appropriate, will be included in the summaries of relationship and severity.

In the AE data listings, all AEs will be displayed.

Laboratory data include analytes for chemistry and hematology, and these will be summarized by treatment and visit for the Safety Population. Descriptive summaries of actual values and changes from Baseline will be presented by study visit and last available assessment for each clinical laboratory analyte and each treatment group. 95% confidence intervals will be presented for change from Baseline.

Laboratory values will be displayed in the data listings with their corresponding normal ranges, and those values that are outside the normal range will be flagged. For each laboratory analyte, shifts in assessments of abnormality from Baseline to each scheduled time point will be presented in shift tables.

A by-patient listing of all clinical laboratory data will also be provided.

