- Change from Baseline in the PROMIS score for sleep disturbance at each post-randomization clinic visit
- Change from Baseline in the PROMIS score for fatigue at each post-randomization clinic visit
- Change from Baseline in the PROMIS fatigue symptom questions 1,3,4 (individually and summed) at each post-randomization clinic visit
- Change from Baseline in the PROMIS fatigue impact questions 6,7,8 (individually and summed) at each post-randomization clinic visit
- Change from Baseline in the PROMIS score for cognitive function at each post-randomization clinic visit
- Change from Baseline in the weekly average of the daily diary assessment of sleep quality at Weeks 1-14
- Change from Baseline in the weekly average of the daily diary assessment of worst pain intensity scores at Weeks 1-14
- Change from Baseline in laboratory markers of inflammation
- Change from Baseline to Week 14 in the Post-COVID-19 Functional Status Scale (PCFS)
- Change from Baseline in the total number of the modified Michigan Body Map pain regions identified as having pain at each post-randomization clinic visit
- Change from Baseline in average NRS Long COVID pain intensity across the 7 pain regions in modified Michigan Body Map at each post-randomization visit

- Change from Baseline in average NRS Long COVID pain intensity within the index site region on the modified Michigan Body Map at each post-randomization visit
- Change from Baseline in average NRS Long COVID pain intensity within the worst region for a given visit on the modified Michigan Body Map at each post-randomization visit

As noted above, results of Week 14 are of primary interest, with other time points being exploratory. For PROMIS fatigue, the questions regard symptoms and impacts will be analyzed independently and additional post-hoc analyses may be completed to evaluate how they contribute to the overall score.

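### By a declared change, the SAP reports laboratory safety in listings only, dropping the by-arm change summaries, confidence intervals and shift tables planned in the protocol

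*SAP*

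**What the plan says.** Protocol 7.2.4 lists "Changes from Baseline in clinical laboratory tests" among the safety endpoints. Safety and tolerability are the trial's only secondary objective (protocol 6.2, SAP 3.1.2).

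Protocol 13.7 says how the chemistry and haematology data are to be reported:

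- By arm: "these will be summarized by treatment and visit for the Safety Population".
- Content: "Descriptive summaries of actual values and changes from Baseline will be presented by study visit and last available assessment for each clinical laboratory analyte".
- Precision: "95% confidence intervals will be presented for change from Baseline".
- Categorical change, for each analyte: "shifts in assessments of abnormality from Baseline to each scheduled time point will be presented in shift tables".
- Listings with normal ranges and flags, and a by-patient listing.

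SAP 11.2 retains only the last item: "Laboratory values will be displayed in the data listings with their corresponding normal ranges", with values outside the range flagged, and a by-patient listing of chemistry, haematology and urinalysis. SAP 13 records the removal of laboratory summaries among the changes from the protocol. SAP 3.2.4 still names laboratory tests as part of the safety assessment.

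**The concern.** A listing shows one patient at a time. It can reveal an individual extreme value, but it gives no mean change per arm, no interval around that change, and no count of patients moving from normal to abnormal. A modest drift in an analyte across the active arm, mostly within the normal range, would not be visible. Nor would a small excess of flagged values that no investigator considered important.

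At stake is how well the report can answer the secondary objective for laboratory safety. The primary efficacy analysis, the alpha level and the definition of study success do not depend on it.

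**Working it through.** No power or error-rate calculation applies. The check is a comparison of planned outputs, followed by a count of the data affected.

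**Step 1: planned outputs side by side**

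| Laboratory output | Protocol 13.7 | SAP 11.2 |
|---|---|---|
| By-arm summary of values and changes | Planned | Absent |
| 95% CI for change | Planned | Absent |
| Shift table per analyte | Planned | Absent |
| Listing with ranges and flags | Planned | Kept |
| By-patient listing | Planned | Kept |

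Of the three by-arm outputs, 0 of 3 survive.

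**Step 2: is the SAP consistent with itself?**

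- SAP 11.4 keeps descriptive summaries of vital signs by treatment and time point, with 95% CIs for change. Protocol 13.7 planned the same kind of output for both data types, and only the laboratory one was dropped.
- SAP 8.1.2 still says, for safety data in general, that the last available observation will be summarised. It does not name or exempt laboratory data. SAP 11.2 and SAP 13 are more specific and would govern, but the sentences do not agree.

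**Step 3: does another output fill the gap?**

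- Adverse events: under protocol 12.2.6, post-Screening laboratory abnormalities judged clinically significant are recorded as adverse events. If treatment-emergent, they enter the SAP 11.1 tables. This route is real, but it carries only values that pass a clinical judgement.
- Exploratory efficacy: SAP 10.2.2 analyses "Change from Baseline in laboratory markers of inflammation" by treatment. The markers are not named. ESR, an obvious candidate, is measured at Screening only (protocol Table 2 footnote and Table 3), so no change can be computed for it. This analysis does not deliver the laboratory safety endpoint.

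What remains unsummarised by arm is group change, shifts, and out-of-range values not judged clinically significant.

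**Step 4: how much data is affected?**

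Inputs come from protocol Table 3 and protocol 12.2.6. I left out Screening-only tests and the conditional free T4, counted direct and total bilirubin separately, counted albumin and total protein separately, and counted each white-cell type once.

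- Repeated analytes: 19 chemistry + 14 haematology = 33.
- Visits: Screening, Week 6, Week 14/ET = 3.
- At the planned 470 patients: 33 × 3 × 470 = 46,530 values.
- At 100 patients, an assumption for illustration because the documents give no achieved number: 33 × 3 × 100 = 9,900 values.

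Both are ceilings. They assume every patient has every test at every visit, whereas patients drop out and a telephone Week 14 visit requires no laboratory tests (protocol 11.6.1).

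For comparison, the restored table would hold 33 analytes × 3 time points (Week 6, Week 14, last available) × 2 arms = 198 mean changes with intervals.

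**The case against.** The strongest reply is that this is a declared simplification of a Phase 2 trial. Protocol 13 leaves the complete description of the analysis to the SAP, and SAP 13 states the change openly. The same list refers to low patient counts over many sites, and SAP 8.1.1.1 includes a proof-of-concept criterion. The text before that list is not in the public copy, so a reason may be given there. Out-of-range values are flagged in the listings, and the clinically important ones reach the adverse event tables.

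Most of this stands, and it rules out several stronger readings that a reader might infer:

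- *That the SAP silently contradicts the protocol.* It does not; SAP 13 discloses the change.
- *That no laboratory abnormality will be counted by arm.* Those recorded as treatment-emergent adverse events will be.
- *That laboratory tests are the one safety endpoint without a by-arm summary.* Physical and oral examination findings are listings only in SAP 11.5, and protocol 13.7 already planned them that way. Laboratory data differ in that a planned by-arm summary was removed entirely.
- *That a between-arm test was lost.* Protocol 13.7 planned descriptive summaries with intervals for change within arm, not a test or an estimated difference.
- *That removing the tables saves nothing because laboratory data are modelled anyway.* The inflammation markers are unnamed and may be few, so SAP 10.2.2 says little about the effort for 33 analytes.

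Disclosure does not, however, supply the by-arm result. Small numbers alone would not explain keeping the vital signs summaries while dropping the laboratory ones.

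**Conclusion.** The point holds as a disclosed loss of descriptive safety reporting: a protocol safety endpoint keeps its listings but loses all three by-arm outputs planned for it. The adverse event route covers part of the gap, namely abnormalities judged clinically significant.

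The value counts show how much would have to be read line by line; they do not measure harm. They rest on complete attendance and, for the smaller figure, on an assumed 100 patients.

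This is an inexpensive improvement worth making, not a threat to the trial's validity. The conclusion assumes that SAP 11.2 and SAP 13 govern over the general sentence in SAP 8.1.2. It makes no assumption about the sponsor's reason for the change.

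**What to change.** In SAP 11.2, restore the protocol 13.7 outputs for the Safety population, for chemistry and haematology, at Week 6, Week 14 and last available assessment:

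- a by-arm descriptive table per analyte, with n and mean change from baseline with its 95% CI;
- a by-arm shift table from baseline, using the normal ranges already planned for the listings.

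Keep the listings. Delete or amend the laboratory entry in SAP 13, and make SAP 8.1.2 agree with SAP 11.2 on last-observation laboratory data.

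If the sponsor prefers to leave the tables out, the minimum is to state in the SAP that laboratory safety is assessed from listings and adverse events only, to exempt laboratory data from the SAP 8.1.2 sentence, and to report this as a limitation in the clinical study report.

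The cost is modest programming time and some added table volume. No new data collection is needed.

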11.3 Columbia Suicide Severity Rating Scale (C-SSRS)

The C-SSRS is an instrument that measures suicidal ideation and behavior, as represented by the items displayed in the table below.

The number of patients with increase over baseline in suicidal ideation at any time point will be reported. The maximum ideation across all visits for a patient will also be summarized with counts and percentages both for all patients and among patients with an increase in ideation. Likewise, the count and percentage of patients with any suicidal behavior will be reported along with a summary of the most extreme behavior each patient reported.

Category	Items
A) Suicidal Ideation	(1) Wish to be dead (2) Non-specific active suicidal thoughts (3) Active suicidal ideation with any methods (not plan) without intent

	to act
	(4) Active suicidal ideation with any some intent to act, without specific plan
	(5) Active suicidal ideation with specific plan and intent
B) Suicidal Behavior	(6) Preparatory acts or behavior
	(7) Aborted attempt
	(8) Interrupted attempt
	(9) Actual attempt
	(10) Completed suicide
	Suicidal Behavior present (composite of items 6-10)
	Non-Suicidal Self-Injurious Behavior

A data listing of C-SSRS results will include only patients with suicidal ideation, suicidal behavior, or self-injurious behavior without suicidal intent at any visit. For patients with suicidal ideation, suicidal behavior, or self-injurious behavior without suicidal intent at any time, data from all visits will be displayed.

11.4 Vital Signs

Descriptive summaries (mean, SD, median, minimum, and maximum) of actual values and changes from baseline at each assessment time point and last available assessment will be calculated for vital signs including weight, BMI, body temperature, pulse rate, systolic blood pressure and diastolic blood pressure. 95% confidence intervals will be presented for change from baseline.

These summaries will be presented by treatment and assessment time for the Safety population. ET data will be analyzed with the closest visit that does not have a valid assessment value.

11.5 Physical Examination and Oral Cavity Exam

A standard physical examination will be performed at Screening, Baseline, and Week 14. In addition, a separate examination of the oral cavity will be performed at each visit (Screening through Week 14). Oral cavity examination findings will be documented separately from other physical examination findings. Note that the oral exam did not include examination of the pharynx; any findings there would be recorded with the physical exam, and also on the AE page, if appropriate.

A data listing of the results at each scheduled visit will be presented for both the standard physical examination and the examination of the oral cavity.

12. MEDICATIONS

12.1 Concomitant Medication

All medications will be coded using a current version of the World Health Organization Drug Dictionary. Prior and concomitant medications will be summarized by treatment group and by the number and percentage of patients taking each medication, classified by using WHO-DD Anatomical Therapeutic Chemical Levels 1 and 3 and preferred term.

Prior medications are defined as medications or therapies initiated prior to the start of the study drug and terminated prior to the start of study drug. Hence, these medications or therapies will have end dates prior to the first dose date of study drug. Concomitant medications are defined as any medications other than the study drug that a patient receives concurrently with the study drug. These medications will have end dates on or after the first dose date of the study drug.

Prior and Concomitant medications will be summarized. All medications will be presented in a listing.

Please refer to [Section 8.3](#) to impute the partial start date and end date of concomitant medication.

12.2 Opioid Medications

A list of patients' concomitant medication records from the CRF data identifying opioid usage will be reviewed by the project team and approved by the sponsor prior to database lock. This listing will be used to flag opioid records in the analysis database and in the by- patient concomitant medication listings.

12.3 Exposure and Compliance

The treatment duration will be calculated and summarized based primarily on CRF data for first and last dose dates (number of days=last dose date – first dose date+1). If these values are missing or patients' diary data indicate dates that exceed this period, the diary dates will be utilized.

Days of exposure will be based on patients' responses to the daily questions regarding medication usage. The number of days on study drug is the total number of days a patient responds that study drug was taken. If the CRF data for the last dose date is a date not included in the diary, it will be added to the count (this should be true for most completing patients since they do not fill out a diary the day of their last visit). The number of patients with total exposure by visit weeks (≤ 2 weeks, 2 to ≤ 4 , 4 to ≤ 8 , 8 to ≤ 12 , 12 to ≤ 14 and >14 weeks) will be presented. Missing days where the patient did not complete the diary will be treated as though study drug was not taken. Days of exposure will also be calculated for the days on each dose of study drug.

Additionally, the number and percentage of patients that drop back to one tablet per day will be summarized and the week in which they reduced their dose will be tabulated (among those that had a dose reduction).

Compliance will be similarly summarized across all study visits for each treatment arm. Study drug compliance as a percentage will be defined as the exposure days defined above divided by the total number of expected days on treatment multiplied by 100. The expected number of days will be the date of last diary recorded dose-randomization date +1. This compliance reporting

will take into account whether or not they took any medication, but will not account for the number of tablets they took on a given day.

Compliance will be summarized with descriptive statistics by treatment arm. The number and percentages of patients within certain categories of compliance (e.g. < 60%, 60% to < 80%, 80% to \leq 100%, greater than 100%) will also be presented.

A listing of drug accountability data based on CRF data will be provided.

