8.2 Efficacy Assessments

8.2.1 Weekly Average of Daily Worst Long COVID Pain Intensity Score

The daily eDiary is an important aspect of this study, and all patients must receive training explaining what is being asked of them, when to complete the diary, and how to use the diary system effectively. Patients will be trained on use of the diary system at Visit 1. Additionally, patients should complete the training on accurate pain reporting and placebo response reduction training as required.

During the 7-day run-in Phase (7 days immediately preceding Visit 2 [Baseline/Randomization Visit; Day 1]) patients will be asked to record their worst daily Long COVID pain intensity on the 11-point (0–10) NRS scale using 24-hour recall and to assess sleep quality from the previous evening, also using an 11-point NRS scale. The average of the 7 days immediately preceding Visit 2 (Baseline Randomization Visit; Day 1) will serve as the Baseline pre-treatment scores.

During the treatment phase, each evening, the system will prompt the patient to reflect on the past 24 hours and record their worst pain intensity, assess their sleep quality from the previous evening, and log study drug dosing from the previous night (post-randomization).

Patients will receive instructions and a password that uniquely identifies them when they log into the diary system, along with instructions about what to do if they have difficulty completing the diary.

The diary should be started the evening of Visit 1 and completed daily until Visit 6 (Week 14). Patients should be instructed to complete the diary in the evening before dosing. Once the patient has properly identified themselves, the diary will prompt answers to the following:

- Rate your worst Long COVID pain intensity during the last 24 hours on a scale from 0–10, where 0 is “no pain” and 10 is “pain as bad as you can imagine”. Rate your sleep quality last night on a scale from 0–10 where 0 is the “best possible sleep” and 10 is the “worst possible sleep”.

After randomization to study drug at Visit 2, the following questions will be added to the daily diary (starting in the evening of the day after randomization, Day 2):

- Did you take your study drug last night? (Yes/No)
- If yes, how many tablets of study drug did you take last night? (1 tablet/2 tablets)

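### The compliance formula in SAP 12.3 can score a perfect completer at 101%, and it measures adherence only up to the last dose

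*SAP*

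**What the plan says.** SAP 12.3 (Exposure and Compliance) defines compliance as "exposure days defined above divided by the total number of expected days on treatment multiplied by 100".

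- **Numerator.** "The number of days on study drug is the total number of days a patient responds that study drug was taken". Then: "If the CRF data for the last dose date is a date not included in the diary, it will be added to the count". The SAP comments that "this should be true for most completing patients since they do not fill out a diary the day of their last visit". Days with no diary entry count as drug not taken.
- **Denominator.** "The expected number of days will be the date of last diary recorded dose-randomization date +1". The CRF last-dose date plays no part here.
- **Tablets.** The measure "will not account for the number of tablets they took on a given day".
- **Categories.** The example bands include one above 100%.

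SAP 8.2.1 sets the timing. The evening diary asks whether drug was taken the previous night, "starting in the evening of the day after randomization, Day 2". An entry on Day d therefore records the dose of Day d-1.

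**The concern.** There are two separate problems.

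1. The two parts of the ratio can end on different days. The CRF day is added on top but not underneath, and the SAP itself expects this for most completers. Full adherence then scores above 100%, a single missed dose is masked, and perfect completers land in a band that a reader would naturally take to mean overuse.

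2. The denominator ends at the last recorded dose. Days after a patient stops taking drug never enter it. A gap in dosing lowers the percentage in mid-study but not at the end of dosing.

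At stake is how the compliance table is read beside the Week 14 result. SAP 10.1.1 analyses data as observed for all intercurrent events, so diary scores recorded off drug can contribute to the Week 14 estimate. A compliance figure that does not register stopping is of little help in judging that.

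**Working it through.** The documents give no compliance figure to reproduce, so this is a count of days from the definitions.

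**Inputs**
- First dose on Day 1, the day of randomization (SAP 4).
- Last planned dose on Day 98 (Protocol Synopsis, dosing). Protocol 11.3 gives the two-tablet period as Days 15 to 99; the passages should be reconciled. Day 98 is used here because drug is returned at Visit 6 on Day 99.
- First drug question on Day 2; last entry on Day 98 for a Day 99 visit (SAP 8.2.1). That entry covers the night of Day 97 to 98 (SAP 8.2.2), so the last diary-recorded dose is the Day 97 dose.
- Visit 6 window Day 95 to Day 106 (SAP 8.2.1).

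**Perfect completer, visit Day 99, doses dated to the night taken**
- Exposure = 97 diary doses + 1 CRF dose = 98.
- Expected = 97 - 1 + 1 = 97.
- Compliance = 98/97 = 101.03%.
- Visit on Day 95: 94/93 = 101.08%. Visit on Day 106: 105/104 = 100.96%.

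**Same patient, one earlier dose missed**
- Exposure = 96 + 1 = 97; 97/97 = 100%. The true value is 97/98 = 98.98%.

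**Sensitivity to the dating rule, which the SAP does not state (perfect completer, Day 99)**

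| Date used in denominator | Date used to decide the CRF addition | Result |
|---|---|---|
| night taken | night taken | 98/97 = 101.03% |
| night taken | entry | 97/97 = 100% |
| entry | night taken | 98/98 = 100% |
| entry | entry | 97/98 = 98.98% |

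The SAP's remark about most completers helps to choose. If the addition were decided by entry dates, the Day 98 entry would already cover a Day 98 CRF dose and nothing would be added. The remark makes sense only if diary doses are dated to the night taken. Applied throughout, that dating is the first row.

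**Category above 100%**
- Dated to the night taken, with the last diary-recorded dose on Day L: at most L diary doses over L days, so only the CRF addition can exceed 100%.
- Dated by entry, with the last such entry on Day L: at most L - 1 diary doses plus one, over L, so the category is empty.

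**Patient who doses on Days 1 to 20, then answers no through Day 98**
- Dated to the night taken: 20/(20 - 1 + 1) = 20/20 = 100%.
- Dated by entry, with the Day 20 dose entered on Day 21: 20/21 = 95.2%.
- Against planned days: 20/98 = 20.4%.

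**The case against.** **Definition.** Doses taken over days to the last dose is a legitimate measure of adherence while on drug; persistence is a different quantity. That stands. The Day 20 result is therefore a limit of the measure that needs a label and a companion line, not an arithmetic error.

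**Same cause?** A reader might infer that the mismatched end dates also produce the Day 20 result. They do not. Both parts end on Day 20 there, and aligning the dates leaves 20/20.

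**Is discontinuation hidden?** A reader might infer so. The documents do not support it. SAP 12.3 also reports treatment duration, days of exposure and exposure by weeks, where the Day 20 patient falls between 2 and 4 weeks. SAP 9.1 tabulates withdrawals with reasons. What stands is narrower: the compliance table itself does not show stopping.

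**Is adherence overstated overall?** This too might be inferred, but counting missing diary days as not taken pulls the other way. As an illustration, a fully dosed completer who misses 10 entries before the last scores (87 + 1)/97 = 90.7%.

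**How likely is such a patient?** The protocol has no off-drug follow-up track; those who discontinue are asked to attend an ET visit. But Protocol 10.5 responds to poor dosing with re-counselling and a recorded deviation, Protocol 11.6.2 foresees a lapse in drug use before ET, and SAP 8.2.1 foresees patients lost to follow-up who keep using the diary. The case is possible; the documents do not show that it is common.

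**Alternative reading.** If the last diary-recorded dose meant the last answered drug question, the Day 20 patient would score 20/97 = 20.6%. The text refers to a dose, not an entry.

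**Conclusion.** The mismatch is real as written. It is worth about one percentage point for a completer with full diary data, and it rests on dating diary doses to the night taken, the reading that fits the SAP's own remark. The category above 100% then identifies no overuse; any patient in it is there because of the CRF addition.

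The second point holds under either dating rule: the percentage describes adherence up to the last dose, so a patient who stops early but keeps answering the diary can score 95% to 100% after dosing on 20.4% of planned days. That figure assumes no earlier missed doses or entries.

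A reader might carry this through to the efficacy result. The documents do not support that: no analysis population, estimand or test uses compliance. The net direction of bias in the table is not established. This is a minor correction to a descriptive output.

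**What to change.** In SAP 12.3:

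1. State that diary doses are dated to the night taken.
2. Use one last-dose date, the later of the CRF and diary dates, in both numerator and denominator. The perfect completer then scores 98/98 = 100% and the patient with one missed dose 97/98 = 98.98%.
3. Drop the category above 100%, or base it on tablet counts.
4. Label the measure as compliance up to last dose.
5. Add a second line: doses taken divided by days from Day 1 to the day before Visit 6 or the ET visit. The Day 20 patient then shows 20/98 = 20.4%. The period must end the day before the visit; run to a Day 99 visit itself, it would give a perfect completer 98/99 = 99.0%.

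The cost is a few sentences of SAP text, one changed derived variable and one added table line. No new data are needed. The second line may also count off-drug days before a delayed ET visit, so it should be read beside the first and not replace it.
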